4.4 Precautions

The following precautions are to be taken during this study:

1. Subjects should wash their hands with mild soap and water before and after applying study medication and should take care not to transfer the study medication to other body areas, including the eye. [REDACTED]
2. Subjects should allow the treated area to dry [REDACTED].
3. [REDACTED]
4. [REDACTED]
5. The study medication should not be applied to unhealed skin, open skin wounds, cuts, abrasions, infections, exfoliative dermatitis, eczematous or sunburned skin.
6. [REDACTED].
7. [REDACTED]
8. Subjects should avoid contact of the study medication with the eyes and with skin outside the selected treatment area defined by the study physician. In case of accidental exposure, the eyes should be rinsed with plenty of water and get medical care as soon as possible.
9. [REDACTED].
10. [REDACTED].
11. Subjects should limit sun exposure, including sunlamps (non-prescription UV light sources), and avoid tanning beds/booths/parlors.
12. Subjects should consult the investigator with any questions regarding concomitant medications.
13. [REDACTED]
14. [REDACTED].

5. PROCEDURES

5.1 Subject Screening and Enrollment

The study personnel will review the IRB approved informed consent form and assent form, if applicable, with each subject and give the subject an opportunity to have all questions answered before proceeding. The consent/assent form must be signed by each subject and witnessed before the subject is enrolled into the study. A copy of the signed consent/assent will be given to every subject and the original will be maintained with the subject's records. Subjects under the legal age of consent must sign an IRB approved written informed consent/assent in addition to a parent or legally authorized representative.

Subjects that require a wash-out [REDACTED] from their initial informed consent/assent signing must be re-consented before any further study procedures can begin.

5.2 Assignment of Subject Number

Once the subject has consented, met eligibility criteria and is considered enrolled in the study, study staff will assign a subject number to the subject. The subject number will correspond to a computer-generated randomization schedule assigning the number to one of the three study treatment groups. The subject numbers will be assigned sequentially in the order in which subjects are enrolled at each center.

5.3 Demographics/Medical History

A demographic profile and complete medical history will be recorded prior to starting study medication. The medical history will include a complete review of all current diseases and their respective treatments.

5.4 Concomitant Medications

Concurrent medications and any medications taken [REDACTED] prior to signing informed consent/assent will be recorded as prior/concomitant medications (using their generic name, if known) with the corresponding indication. The medications to be recorded will include prescription (Rx) and over-the-counter (OTC) medications and dietary supplements. All medications taken on either a regular or "prn" basis, including vitamins, aspirin and acetaminophen, should be recorded on this page prior to commencing the use of the study medication.

5.5 Physical Examination

The investigator, sub-investigator or appropriately delegated and qualified designee will perform a brief physical examination [REDACTED] prior to the subject starting study medication. [REDACTED]

5.6 Urine Pregnancy Test

Females of childbearing potential (excluding women who are surgically sterilized or post-menopausal for at least 2 years), in addition to having a negative urine pregnancy test, must be willing to use an acceptable form of birth control during the study. [REDACTED]

[REDACTED]

5.7 Dermatological Assessment (Diagnosis)

The investigator or sub-investigator will examine the subject to establish the clinical diagnosis of Actinic Keratosis defined as the presence of 4 to 8 clinically typical, visible, discrete, nonhyperkeratotic, nonhypertrophic Actinic Keratosis lesions, contained within a contiguous 25cm² area on the trunk or extremities.

5.8 Fitzpatrick Classification Scale

The Fitzpatrick skin scale classifies a person's complexion and their tolerance of sunlight. It is commonly used by many practitioners to determine how someone will respond or react to dermatological treatments, and how likely they are to get skin cancer.

At Visit/Day 1 (Baseline), the Principal Investigator (PI) or Sub-Investigator (Sub-I) will examine the subject's skin to determine the skin type by using the Fitzpatrick scale below and will indicate the skin type on the source document and eCRF.

Skin Type	Skin Color	Characteristics
I	White; [REDACTED]	[REDACTED]
II	White; [REDACTED]	[REDACTED]
III	Cream [REDACTED]	[REDACTED]
IV	Brown; [REDACTED]	[REDACTED]
V	Dark Brown; [REDACTED]	[REDACTED]
VI	Black	[REDACTED]

5.9 Clinical Actinic Keratosis Lesion Counting & Assessment

Each subject's initial condition and course of Actinic Keratosis will be assessed by counting the number of lesions located within the designated treatment area on the trunk or extremities. At Visit 1/Day 1 (Baseline), the PI or qualified study staff should select an area of 25cm² (may be of

[REDACTED]

any shape, [REDACTED] to be treated with the study medication gel as the designated treatment area on the trunk or extremities. This selected treatment area should have 4 to 8 visible clinically discrete Actinic Keratosis lesions. Additionally, the PI or designated staff will document the location of each lesion, the designated treatment area, and the size (in cm²) of the treatment area at Visit 1/Day 1 (Baseline) will be marked in the subject's source documentation [REDACTED]

[REDACTED]

To the greatest extent possible, the same investigator who made Visit 1/Day 1 (Baseline) assessments will perform evaluations at Visit 4/Day 57. At Visit 1/Day 1 (Baseline), Visit 4/ Day 57, and Unscheduled Visit, if applicable, the number of Actinic Keratosis lesions within the treatment area will be counted and recorded in the source documentation and eCRFs. Additionally, at Visit 4/Day 57, and Unscheduled Visit, if applicable, new Actinic Keratosis lesions as compared to Visit 1/Day 1 (Baseline) will be counted and recorded in the source documentation and eCRFs. [REDACTED]

[REDACTED]

Complete clearance (Actinic Keratosis lesion count in the selected treatment area) at Visit 4/Day 57 will be assessed. Complete clearance is defined as absence of clinically visible Actinic Keratosis lesions (including presence of new lesions) in the selected treatment area at Visit 4/Day 57. The investigator or sub-investigator will confirm the number of lesions in the selected treatment area (including new lesions) and clinical response success if lesion count is equal to zero at Visit 4/Day 57.

[REDACTED]

Lesion counting must be conducted by qualified investigators or designated staff listed on the Form FDA 1572 who have been delegated these tasks by the PI. [REDACTED]

[REDACTED]

[REDACTED]

5.10 Application Site Reaction Assessment

To the greatest extent possible, the same investigator who made Visit 1/Day 1 (Baseline) assessments will assess the application site reactions, grade them according to a 5-point scale and a designated staff will record them in the source document and eCRFs at each subsequent visit. This assessment must be conducted by qualified individuals listed on the Form FDA 1572 who have been delegated this task by the PI. [REDACTED]

At baseline (prior to initial dosing) and each subsequent visit, application site reactions of erythema, flaking/scaling, crusting, swelling, vesiculation/pustulation, and erosion/ulceration are to be recorded in the source document and eCRFs.

Application site reactions (erythema, flaking/scaling, crusting, swelling, vesiculation/pustulation, and erosion/ulceration) are not to be recorded as adverse events unless they result in either:

- The temporary discontinuation of the study medication.
- The discontinuation of the subject from the study.
- The use of a new concomitant medication in order to treat this event.

Any other application site reaction not listed above (such as pain, pruritus and infection) should be recorded as adverse events in the source document and eCRFs.

The following scale will be used for the Application Site Reaction Assessment:

Site Reaction	Description
Erythema	[REDACTED]
Flaking/scaling	[REDACTED]
Crusting	[REDACTED]
Swelling	[REDACTED]
Erosion/ulceration	[REDACTED]
Vesiculation/Pustulation	[REDACTED]

Site Reaction	Grading Criteria				
	0	I	I	I	I
██████████	██████████	██████████	██████████	██████████	██████████
██████████ ██████████	██████████	██████████ ██████████	██████████	██████████	██████████ ██████████
██████████	██████████	██████████	██████████	██████████	██████████ ██████████
██████████	██████████	██████████ ██████████	██████████ ██████████ ██████████	██████████ ██████████	██████████ ██████████ ██████████
██████████ ██████████	██████████	██████████ ██████████	██████████ ██████████ ██████████	██████████	██████████ ██████████
██████████ ██████████	██████████	██████████	██████████ ██████████ ██████████	██████████ ██████████ ██████████	██████████ ██████████ ██████████ ██████████

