5.11 Study Medication Use, Patient Instructions and Diary

Each subject’s drug kit box contains █████ 0.47 gram tubes. At the baseline visit, the subject will apply the contents of one of the tubes at the site under study staff supervision and that tube will be placed back in the drug kit box. The second tube will be given to the subject to take home with them for their second application along with a diary. Their Day 2 application should be applied at approximately the same time as the Day 1 application. Additionally, the study staff must ensure subjects understand the instructions for applying the study medication and refrigerate the study medication at home all times.

Subjects must not use the study medication for more than 2 consecutive days.

At Visit 2/Day 3 the study medication will be collected to visually assess compliance. Compliance will also be determined from the diary, in which the subject will be instructed to record if they applied their second dose of medication or not. After the compliance evaluation, empty, filled and partially used tubes will be collected and kept by the site.

Subjects will wash the designated treatment area with a mild soap by using only the hands and pat dry with a soft towel █████ before applying the study medication. The study medication from one tube will be applied to the selected treatment area, one contiguous skin area of 25 cm² area. After spreading the study medication █████ over the treatment area, █████. Subjects should wash their

hands with mild soap and water immediately after applying the study medication gel and take care not to transfer the applied study medication gel during and after application to other areas, including the eyes. If the treatment area is on the back of the hands (not palm), the subject should wash only the fingertip which was used for applying the gel. [REDACTED]

[REDACTED]

Subjects will be instructed to not use any other topical treatments or products other than the study medication gel or approved moisturizer in the selected treatment area during the two-day treatment period.

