7.2 Definitions

An adverse event (AE) is defined as any untoward medical occurrence in a patient administered a medicinal product and which does not necessarily have to have a causal relationship with this treatment. An adverse event can therefore be any unfavorable and unintended sign (for example, an abnormal laboratory finding), symptom, or disease temporally associated with the use of a medicinal product, whether or not considered related to this medicinal product.

A serious adverse event (SAE) is an adverse event that results in any of the following outcomes:

- death
- life-threatening event (i.e., the subject was, in the opinion of the investigator, at immediate risk of death from the event as it occurred. It does not include an event that, had it occurred in a more severe form, might have caused death)
- requires in-subject hospitalization or prolongs hospitalization
- a persistent or significant disability/incapacity or substantial disruption of the ability to conduct normal life functions
- congenital anomaly/birth defect
- Other adverse events that may be considered serious when, based upon appropriate medical judgment, they may jeopardize the patient or subject or may require medical or surgical intervention to prevent one of the previously listed outcomes.

Immediately Reportable Adverse Events (IRAE): Any serious AE or any AE that necessitates discontinuation of study medication, including pregnancy.

Unexpected Adverse Event: An unexpected event is any adverse drug experience, the specificity or severity of which is not consistent with the current approved product labeling (package insert, Appendix D) for the study medication, the Investigator's Brochure, or as described in the clinical protocol and consent materials.

Intensity of Adverse Events: The maximum intensity of an AE during a day should be recorded on the eCRF. If the intensity of an AE changes over a number of days, then separate entries should be made having distinct onset dates for the changes in severity.

Mild - AEs are usually transient, requiring no special treatment, and do not interfere with subject's daily activities.

Moderate - AEs typically introduce a low level of inconvenience or concern to the subject and may interfere with daily activities, but are usually ameliorated by simple therapeutic measures.

Severe - AEs interrupt a subject's usual daily activity and traditionally require systemic drug therapy or other treatment.

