7.4 SAE & AEs Requiring Discontinuation of Study Drug, including Pregnancies

ANY SAE, WHICH OCCURS AFTER A SUBJECT HAS ENTERED THE STUDY, WHETHER OR NOT RELATED TO STUDY MEDICATION, MUST BE REPORTED TO [REDACTED] AND PERRIGO IMMEDIATELY (WITHIN 24 HOURS) VIA TELEPHONE OR FACSIMILE. IF INITIALLY REPORTED VIA TELEPHONE, THIS MUST BE FOLLOWED-UP BY A FACSIMILE OF THE WRITTEN SAE REPORT WITHIN 24 HOURS OF THE CALL TO [REDACTED].

Non-serious events that require discontinuation of study medication (including laboratory abnormalities) should be reported to Perrigo immediately and within 1 working day. Subjects who discontinue due to experiencing adverse events should be followed clinically until their health has returned to baseline status, or until all parameters have returned to normal. It is expected that the investigator will provide or arrange appropriate supportive care for the subject.

A subject who experiences a severe adverse event related to study drug will be discontinued from the study.

The notification about any serious adverse event should be directed to:

[REDACTED]
[REDACTED]

[REDACTED]

[REDACTED]

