5.6 Safety Variables and Analyses

Duration of Treatment and Medication Compliance

Number of applications, days of exposure, and compliance rate will be summarized by treatment group using descriptive statistics. For each subject, the overall duration of treatment (days) will be calculated using the following formula:

$$\text{(Date of last application of study medication)} - \text{(Date of first application of study medication)} + 1.$$

Medication compliance rate (%) will be calculated for each subject as follows:

$$\text{(Total number of applications used)} / \text{(Expected number of applications)} * 100\%.$$

Subjects who complete the study are expected to have 2 applications. [REDACTED]

[REDACTED] For prematurely discontinued subjects, expected number of applications will be determined based on the

overall duration of treatment by the time of discontinuation. Descriptive summaries of exposure and medication compliance rate will be provided by treatment group for the ITT subjects

Adverse Events

Adverse events (AEs) will be coded in MedDRA, version 15.1. Treatment-Emergent Adverse Event (TEAE) is defined as any AE occurs on or after applying the first dose of study drug. Number and percent of subjects reporting TEAEs will be tabulated by treatment group. Summaries will be presented by body system and preferred term for the ITT population, and further by severity and relationship to study medication. TEAEs reported by 5% or more subjects for any treatment group will also be summarized. In the summaries of incidence rates (frequencies and percentages), severity and relationship to study drug, subjects who report more than one event that are mapped to the same preferred term will be counted only once under the strongest severity and relationship, accordingly Fisher's exact test will be used to compare the proportions of subjects of the two active treatment groups who report any TEAE.

Treatment-Emergent Serious Adverse Events (TESAEs) will be discussed within the clinical study report. TESAEs and TEAEs that led to treatment interruption or discontinuation will be presented in data listings.

Concomitant Medications

Concomitant medications will be coded using the WHO Drug Dictionary, version September 2014, and will be presented in data listings.

Application Site Reactions

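### Protocol 5.10 has no AE trigger for a local skin reaction that leads a subject to omit the second of two doses, and it is not reconciled with the Section 7 reporting rules

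*Protocol*

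**What the plan says.** Protocol 5.10 covers erythema, flaking/scaling, crusting, swelling, vesiculation/pustulation and erosion/ulceration. These are graded at baseline and at every later visit, but they "are not to be recorded as adverse events unless they result in either" one of three things:

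- "The temporary discontinuation of the study medication"
- departure from the trial altogether
- a new medicine taken to treat the reaction

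Other site reactions, such as pain, pruritus and infection, are always AEs.

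On dosing, Protocol 5.11 has the subject apply the first tube at the site on Day 1 and take the second home for Day 2. It adds: "Subjects must not use the study medication for more than 2 consecutive days". Protocol 5.16 counts a dose as missed if it is not applied on its day, and treats one missed dose as non-compliance.

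On reporting, Protocol 7.2 defines an AE broadly, with no exception for site reactions. It makes immediately reportable "Any serious AE or any AE that necessitates discontinuation of study medication, including pregnancy". Section 7.3 requires all AEs under that definition to be reported. Section 7.4 requires every SAE to be reported within 24 hours, and non-serious events that require stopping the drug to reach the sponsor within one working day.

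On analysis, SAP 5.6 says: "TESAEs and TEAEs that led to treatment interruption or discontinuation will be presented in data listings". It compares the two active arms on the proportion with any TEAE, using Fisher's exact test, and separately tabulates site-reaction severity by arm and visit.

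**The concern.** The three triggers suit a long course in which treatment can be paused and resumed. Here there are only two doses. The trigger for stopping drug names the kind of stop that can hardly happen and leaves out the kind that can. Seriousness is not a trigger either, and 5.10 does not refer to Section 7.

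Local skin reactions are this product's expected toxicity; Protocol 7 warns that severe vesiculation/pustulation and erosion/ulceration can occur. Safety equivalence is to be judged on the nature, severity and frequency of AEs, and the only planned safety test between test and reference is on any TEAE. If a tolerability stop is recorded as poor adherence, the comparison and the discontinuation listing both miss it. Sites that read 5.10 and Section 7 differently may also classify the same event differently.

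**Working it through.** The documents give no figure to reproduce on this point. The check sets the passages side by side, with one line of arithmetic.

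**1. Which dose can a reaction cost?** Dose 1 is applied under supervision on Day 1 and dose 2 is due on Day 2 (5.11). A reaction to treatment can therefore cost only dose 2.

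**2. Can that stop be temporary?** A dose not applied on Day 2 is already missed (5.16), and the medication is collected at Visit 2/Day 3 (5.11). Under these rules there is almost no room for a pause followed by resumption, so the first trigger fits almost no case.

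**3. Does the protocol itself allow the case to arise?** Yes. Precaution 5 in Protocol 4.4 says that the medication should not go on unhealed skin or open wounds. A subject with an open reaction after dose 1 could omit dose 2 by following that precaution.

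**4. Possible outcomes when dose 2 is omitted because of a listed reaction**

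| Outcome | Trigger met in 5.10 | Recorded as AE |
|---|---|---|
| Subject leaves the study | Second | Yes |
| New medication is given for the reaction | Third | Yes |
| Subject stays, no new medication | None as worded | No |

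**5. How the third row appears in the analysis.** SAP 5.6 defines compliance as applications used / applications expected × 100%, with 2 expected for a subject who completes the study:

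1 / 2 × 100% = 50%

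The subject is classed as non-compliant. With no AE record there is no TEAE, so the subject is absent from the listing of events that led to interruption or discontinuation. The subject counts in the any-TEAE proportion only if some other AE is recorded.

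**6. Does Protocol 5.17 close the gap?** Not clearly. Its ground for removal because of stopping treatment starts from an adverse event, which is the status that 5.10 withholds. Removal for non-compliance is possible and would arguably meet the second trigger, but the stated reason could then be non-compliance and not the reaction.

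**7. Serious reactions.** By 7.2 an SAE is an AE with a serious outcome, and 7.3 and 7.4 require reporting without exception. Section 7.3.1 wants the AE eCRF term and the SAE report to match exactly. For a serious listed reaction that meets none of the three triggers, 5.10 bars the AE entry that 7.3.1 presupposes. No visible text says which section prevails.

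**The case against.** The strongest reply is that 5.10 is only a recording convention and that Section 7 does the real work. Much of this stands:

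- **Serious reactions.** A reader might infer that they fall outside the SAE data. The documents do not support that. The AE definition in 7.2 has no exception for site reactions, 7.3 refers to that definition, and 7.4 covers every SAE. The fault is an unresolved conflict between sections, not the lack of a rule that captures these events.
- **Non-serious reactions that stop drug.** The sentence in 7.4 speaks of events, so there is an arguable route to the sponsor. Notification does not by itself create a TEAE record, however, and the SAP listing draws only on TESAEs and TEAEs.
- **Circularity.** A reader might see a circle, because 7.4 says "A subject who experiences a severe adverse event related to study drug will be discontinued from the study" while 5.10 makes departure from the study a condition for AE status. This does not hold. Section 5.17 gives grounds for removal that need no AE, including withdrawn consent, worsened condition and investigator discretion. By the 7.2 definition, severe events traditionally require systemic drug therapy or other treatment, so the new-medication trigger would usually apply first.
- **Data loss.** The reactions are graded at every visit, including Day 3, and missed doses are recorded. What is lost is AE status and the link between the reaction and the omitted dose. A severity table by visit does not show that link.
- **Effect on the Fisher test.** Pain and pruritus are always AEs and are among the common reactions, so some affected subjects may already count as having a TEAE.
- **Redaction.** Text is blacked out in 5.10 ahead of the trigger list, in 5.16, 5.17 and the Visit 2 procedures, and in SAP 5.6 after the expected number of applications. A rule for a withheld dose could sit there. The trigger list itself is fully visible.

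**Conclusion.** The concern holds in a limited form. As worded, 5.10 leaves without an AE record the subject who omits dose 2 because of a listed reaction, remains in the study and takes no new medication. That tolerability stop appears as 50% compliance, is absent from the SAP discontinuation listing, and enters the any-TEAE comparison only through some other AE. For serious reactions the finding is narrower: 5.10 and Sections 7.2 to 7.4 give conflicting instructions that must be reconciled.

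The number of subjects affected cannot be estimated, because the documents give no event rates. The rule applies alike in all arms of a blinded trial, so no direction of bias between test and reference can be derived. The conclusion assumes that the redacted text contains no rule for a dose withheld because of a reaction, and that sites do not read an omitted dose 2 as a temporary stop. It is more than a missing detail, because a stated recording rule misclassifies the event.

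**What to change.** Make three changes in Protocol 5.10, and carry them into the eCRF completion guide:

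1. Reword the first trigger as: *temporary or permanent discontinuation of study medication, including omission of the second application because of the reaction*.
2. Add a trigger: *or meets a seriousness criterion in Section 7.2*.
3. State that Sections 7.2 to 7.4 govern the reporting of such events.

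These changes affect recording only and leave dosing and clinical management as they are. The cost is a few lines of text. The downside is that somewhat more AEs will be recorded.
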